11.3.1.1 Serious Adverse Events

All adverse events will be reviewed by the Principal Investigator, [name], and will be reported to Partners IRB and to the Human Research Committee (HRC) in accordance with HRC Guidelines. A serious adverse event (SAE) is defined as an adverse event that meets any of the following criteria:

1. Results in death.
2. Is life threatening: that is, poses an immediate risk of death as the event occurs.
 - This serious criterion applies if the study subject, in the view of the PI, is at immediate risk of death from the AE as it occurs. It does not apply if an AE hypothetically might have caused death if it were more severe.
3. Requires inpatient hospitalization or prolongation of existing hospitalization.
 - Hospitalization for an elective procedure or a routinely scheduled treatment is not an SAE by this criterion because an elective or scheduled "procedure" or a "treatment" is not an untoward medical occurrence.
4. Results in persistent or significant disability or incapacity.
 - This serious criterion applies if the "disability" caused by the reported AE results in a substantial disruption of the subject's ability to carry out normal life functions.
5. Results in congenital anomaly or birth defect in the offspring of the subject.
6. Necessitates medical or surgical intervention to preclude permanent impairment of a body function or permanent damage to a body structure.
7. Important medical events that may not result in death, are not life-threatening, or do not require hospitalization may also be considered SAEs when, based upon appropriate medical judgment, they may jeopardize the subject and may require medical or surgical intervention to prevent one of the outcomes listed in this definition. Examples of such medical events include blood dyscrasias or convulsions that do not result in inpatient hospitalization.

An inpatient hospital admission in the absence of a precipitating, treatment-emergent, clinical adverse event may meet criteria for "seriousness" but is not an adverse experience and will therefore not be considered an SAE. An example of this would include a social admission (subject admitted for reasons other than medical, e.g., lives far from the hospital, has no place to sleep).

The PI is responsible for classifying adverse events as serious or non-serious and determining if there is reasonable possibility that the drug was the cause.

11.3.2 Assessment and Recording of Adverse Events

The PI will carefully monitor each subject throughout the study for possible AEs. All AEs will be documented on CRFs designed specifically for this purpose. All AEs will be collected and reported in the EDC system.

11.3.3 Assessment of Adverse Events

At each visit (including telephone visits), the subject will be asked if they had any problems or symptoms since their last visit in order to determine the occurrence of adverse events. If the subject reports an adverse event, the Investigator will probe further to determine:

- Type of event
- Date of onset and resolution (duration)
- Severity (mild, moderate, severe)
- Seriousness (does the event meet the above definition for an SAE)
- Causality, relation to investigational protocol
- Outcome

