3.3 Study Outcome Measures

3.3.1 Safety Measure Outcomes

Medical history, adverse events, and classic metabolic, hematologic, coagulation, and immune blood labs will be collected at Screening to determine eligibility. Adverse events will be solicited at every visit. Hematologic and coagulation blood labs will be repeated at Week 12 and Week 52 visits for LP safety. Vital signs will be measured at all in-person visits. Additionally, four weeks after the first injection, we will assess the injection site and evaluate for any signs of systemic infection prior to second BCG vaccination in the other arm. Vaccination sites will also be assessed at Weeks 12, 26, and 52. We will use the FDA Toxicity Grading Scale, as performed in vaccine trials, to denote changes from baseline. Safety measures, including updated medical history and adverse events, will also be collected at Week 78 and Week 104.

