11.3 Adverse Event Reporting Guidelines

11.3.1 Adverse Event

An adverse event (AE) is any unfavorable and unintended sign (including a clinically significant abnormal laboratory finding, for example), symptom, or disease temporally associated with a study, use of a drug product or device, whether or not considered related to the drug product or device.

Examples of adverse events include: new conditions, worsening of pre-existing conditions, clinically significant abnormal physical examination signs (i.e. skin rash, peripheral edema, etc.), or clinically significant abnormal test results (i.e. lab values or vital signs), with the exception of outcome measure results, which are not being recorded as adverse events in this trial (they are being collected, but analyzed separately). The BCG vaccine causes a circular and contained inflammatory response with scab followed by scar formation. For this study, this expected BCG vaccine site reaction is not considered an adverse event. Stable chronic conditions (e.g. arthritis) that are present prior to the start of the study and do not worsen during the trial are NOT considered adverse events. Chronic conditions that occur more frequently (for intermittent conditions) or with greater severity are considered as worsened and therefore would be recorded as adverse events. Adverse events are generally detected in two ways:

- Clinical → symptoms reported by the subject or signs detected on examination.
- Ancillary Tests → abnormalities of vital signs, laboratory tests, and other diagnostic procedures (other than the outcome measures, the results of which are not being captured as AEs).

If discernible at the time of completing the AE log, a specific disease or syndrome rather than individual associated signs and symptoms should be identified by the PI and recorded on the AE log. However, if an observed or reported sign, symptom, or clinically significant laboratory anomaly is not considered by the PI to be a component of a specific disease or syndrome, then it should be recorded as a separate AE on the AE log. Clinically significant laboratory abnormalities, such as those that require intervention, are those that are identified as such by the PI.

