Participants will be monitored for adverse events from the time they sign consent until completion of their participation in the study (defined as death, consent withdrawal, loss to follow up, early study termination for other reasons, or following completion of the entire study). An unexpected adverse event is any adverse event, the specificity or severity of which is not consistent with the current product insert.

The study procedures and the well-being of all participants will be monitored closely by the Principal Investigator, [name] MD, and the Co-Investigators [name] DNP, FNP-BC, and [name] M.D., Ph.D. Throughout the course of the study, constant feedback with the subject is maintained in order to assess comfort and safety and to minimize risks throughout the procedure. The above investigators will be responsible for determining if a subject should be removed from the study. Criteria for removal include the following: 1) if a subject is unwilling or unable to participate in study procedures 2) if the subject refuses to participate and consent, 3) if the subject acquires a medical condition that prohibits further participation, 4) if in the opinion of the MGH principal investigator, [name], it is decided that it is not in the subject's best interest to continue participation.

Unanticipated problems including adverse events will be reported to the PHRC as described in the PHRC policy on Unanticipated Problems Involving Risks to Subjects or Others including adverse events.

All data will be managed in compliance with applicable regulatory requirements. The study coordinator, under the supervision of the PI, will collect, transcribe, correct, and transmit the data onto source documents, Case Report Forms (CRFs), and/or other forms used to report, track, and record clinical research data.

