11.3.4 Relatedness of Adverse Event to Investigational Protocol

1. Not Related: Concomitant illness, accident, or event with no reasonable association with protocol.
2. Unlikely: The reaction has little or no temporal sequence from administration of the investigational protocol, and/or a more likely alternative etiology exists.
3. Possibly Related: The reaction follows a reasonably temporal sequence from administration of the investigational protocol and follows a known response pattern to the suspected investigational protocol; the reaction could have been produced by the investigational protocol or could have been produced by the subject's clinical state or by other modes of therapy administered to the subject.
4. Probably Related: The reaction follows a reasonably temporal sequence from administration of investigational protocol; is confirmed by discontinuation of the investigational protocol or by re-challenge; and cannot be reasonably explained by the known characteristics of the subject's clinical state.
5. Definitely Related: The reaction follows a reasonable temporal sequence from administration of investigational protocol; that follows a known or expected response pattern to the investigational protocol; and that is confirmed by improvement on stopping of the investigational protocol, and reappearance of the reaction on repeated exposure.

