11.3.5 Recording of Adverse Events

All clinical adverse events are recorded in the Adverse Event (AE) Log in the subject's study binder. Entries on the AE Log (and into the EDC) will include the following: name and severity of the event, the date of onset, the date of resolution, relationship to investigational product, action taken, and primary outcome of event.

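### AE questions are directed to the participant, with no stated role for the study partner and no scheduled contact or diary for 28-42 days after dose 1 and 37-61 days after dose 2

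*Combined protocol and SAP*

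**What the plan says.** All references are to the combined protocol and SAP.

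- **Who is asked.** Section 11.3.3 says that at each visit, telephone visits included, "the subject will be asked if they had any problems or symptoms since their last visit". Further probing follows if the subject reports something. Section 11.3.1 describes clinical detection as "symptoms reported by the subject or signs detected on examination". Section 3.3.1 is broader and names no source: "Adverse events will be solicited at every visit".
- **Who the participants are.** Section 4.1.1 admits a MoCA of 8 or more and a global CDR from 0.5 to 2. Section 1.3 expects that some participants will be unable to consent for themselves.
- **The study partner.** Section 4.1.1 requires a partner with contact several days a week who can come to visits and inform staff. The partner is used for the CDR (6.4.3), NPI-Q (6.5.1) and FAQ (6.5.2), and for the telephone pre-screen when decision making is impaired (6.2.1.1). No section uses the partner for AEs.
- **When.** Each dose is followed by 30 minutes of monitoring (6.2.2, 6.2.3). The next scheduled AE reviews are Visit 3 and Visit 4 (6.1). No diary is described.
- **What has to be recorded.** The AE log takes "the date of onset, the date of resolution, relationship to investigational product" (11.3.5). Relatedness leans on timing: an event is graded unlikely when "The reaction has little or no temporal sequence from administration of the investigational protocol" (11.3.4), or when another cause is more likely.

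**The concern.** Section 9.1 says that systemic effects such as fever and myalgia, lasting 1-2 days, may occur after BCG. Under the plan, a person who may have moderate dementia is asked about them four or more weeks later and has to supply onset and resolution dates. The required informant, already trusted for three clinical scales, has no stated part in this.

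Safety and tolerability is the first primary objective (3.2). The primary safety endpoint is the incidence of treatment-emergent Grade II-IV AEs (8.2). The all-AE, preferred-term and relatedness tables in 8.2 rest on the same ascertainment, as does the participant count behind the study pause rule in 5.5. A short reaction that nobody records at the time may not be recoverable later.

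**Working it through.** **Inputs.** Visit 3, with dose 2, is 28 (+14) days after dose 1 (6.2.3). Visit 4 is 84 ± 5 days after dose 1 (6.2.4). Systemic effects last 1-2 days (9.1). The sample size is about 15 (8.1).

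**1. The plan's own figure.** Dose 1 to Visit 3 is 28 to 28 + 14 = 42 days. In weeks, 28/7 = 4.0 and 42/7 = 6.0. This reproduces the 4-6 week dose spacing in 3.1. It is also the time from dose 1 to the next scheduled AE contact.

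**2. Dose 2 to Visit 4.** Visit 4 falls between 84 − 5 = 79 and 84 + 5 = 89 days after dose 1.
- Shortest: 79 − 42 = 37 days (5.3 weeks).
- Longest: 89 − 28 = 61 days (8.7 weeks).
- Nominal: 84 − 28 = 56 days (8.0 weeks).

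**3. Time from the end of a short reaction to the question**, assuming onset on the dosing day:
- Dose 1: 28 − 2 = 26 to 42 − 1 = 41 days.
- Dose 2: 37 − 2 = 35 to 61 − 1 = 60 days.

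**4. Roll-over participants (6.1.1).** Those given BCG at the original trial's baseline went through the dose-1 interval under a protocol not shown here, so only the dose-2 interval is at issue. Those first given placebo receive dose 2 about one month after dose 1. Taking 28-31 days as an assumption, dose 2 to Visit 4 is 79 − 31 = 48 to 89 − 28 = 61 days, inside the range in step 2.

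**5. What each failure does to the results.**

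| Short reaction is | AE counts | Dates and relatedness | Primary endpoint |
|---|---|---|---|
| recalled with dates | correct | correct | correct |
| recalled without dates | correct | weakened | unchanged: any event since the dosing visit is treatment-emergent, related or not |
| not recalled | too low | lost | falls only if it reached Grade II and was the participant's sole Grade II-IV event |

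**6. Size for the endpoint.** Reading incidence as the share of participants with at least one such event, one case in the last row that meets both conditions lowers it by 1/15 = 6.7 percentage points.

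The documents do not say how often short reactions reach Grade II or how often they would be forgotten, so no expected under-count can be computed.

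**The case against.** The main point rests on silence. Section 11.3.3 does not say that only the participant is asked, 3.3.1 names no source, the partner may be in the room and may volunteer information, and staff must report changes in a participant's function (5.1). Concomitant medications are reviewed at every contact (6.1), and their use for AEs is a safety endpoint (8.2). Section 6.3.5 allows a site examination after a participant report between visits, and 11.3.1 adds that "constant feedback with the subject is maintained in order to assess comfort and safety". A MoCA of 8 and a CDR of 2 are entry limits, and people with MCI are enrolled too. In a feasibility-sized pilot, one clarifying sentence might seem enough.

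Much of this stands, and it limits the claim to what may be missed. It does not remove the point. The feedback in 11.3.1 is with the subject and has no schedule. The report in 6.3.5 also comes from the subject. Medication review helps only if a medicine was taken and remembered. None of these shortens the intervals, and a clarifying sentence about the partner would not supply dates several weeks later.

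The objection is also right that the primary endpoint is well shielded. It counts treatment-emergent events whether related or not, so misdating alone cannot lower it.

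**Conclusion.** The point holds as an inexpensive improvement worth considering. As written, the plan can under-record short post-vaccination reactions and weaken the dates and relatedness of those it does record. The intervals are exact: 28-42 days after dose 1 and 37-61 days after dose 2. The effect on the primary endpoint is about 6.7 points per qualifying case with 15 participants, and the number of cases is unknown.

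A reader might infer more than the documents support:

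- *That the partner is barred from reporting AEs.* The text gives the partner no role, which is different.
- *That the primary safety endpoint is materially biased.* All three conditions must be met: no recall at all, at least Grade II, and no other such event in that participant. No passage gives a frequency for any of them.
- *That the 3-month pilot shows the problem is real, or absent.* Section 2.1.3 reports only procedure-related AEs and does not say how AEs were asked for, so it fits either few reactions or poor capture.
- *That other denominators bound the effect.* The 12 and 25 in 4.2 are expected completers and an enrolment ceiling. Under 6.2.1.3 anyone who signs consent is enrolled, so neither is a count of people dosed.

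**What to change.** 1. In 11.3.1, 11.3.3 and 6.2.3 to 6.2.9, including the Early Termination Visit, ask both the participant and the study partner at every visit and phone check, in person or by phone. Record events reported by either and note the source.
2. Add a dated symptom diary for 14 days after each dose given under this protocol, completed with the partner's help and collected at the next visit (Visit 3, Visit 4 or Early Termination). It covers the 1-2 day systemic effects and the first skin lesions, which 9.1 places at 10-14 days. It does not cover the papule maximum at 4-6 weeks.

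**Cost.** An IRB-approved amendment. At most two diaries per participant, one for roll-overs already given BCG (so at most 2 × 15 = 30 with 15 participants), with their data entry. A short partner question at each contact; Visit 3 lists no partner activity, so that one may need a call. Some partner reports will be harder to verify, and the AE rate may look less favourable. No extra visit is needed.

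**Related matters to handle separately.**
- Section 11.3.1 states "For this study, this expected BCG vaccine site reaction is not considered an adverse event". Sites are examined and reactivity recorded under 6.3.5, but 8.2 names no summary of these findings by dose. The nearest is physical examination at last visit. Site reactions beyond the expected one do enter the AE tables.
- Severity is described in several ways. Section 3.3.1 says "We will use the FDA Toxicity Grading Scale, as performed in vaccine trials, to denote changes from baseline". Section 5.3.2 applies that scale to local skin reactions, 5.5 equates grade 3 with severe, 8.2 uses MedDRA grading with Grades II-IV, and 11.3.3 has three levels. These passages should be reconciled.

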11.3.4 Relatedness of Adverse Event to Investigational Protocol

1. Not Related: Concomitant illness, accident, or event with no reasonable association with protocol.
2. Unlikely: The reaction has little or no temporal sequence from administration of the investigational protocol, and/or a more likely alternative etiology exists.
3. Possibly Related: The reaction follows a reasonably temporal sequence from administration of the investigational protocol and follows a known response pattern to the suspected investigational protocol; the reaction could have been produced by the investigational protocol or could have been produced by the subject's clinical state or by other modes of therapy administered to the subject.
4. Probably Related: The reaction follows a reasonably temporal sequence from administration of investigational protocol; is confirmed by discontinuation of the investigational protocol or by re-challenge; and cannot be reasonably explained by the known characteristics of the subject's clinical state.
5. Definitely Related: The reaction follows a reasonable temporal sequence from administration of investigational protocol; that follows a known or expected response pattern to the investigational protocol; and that is confirmed by improvement on stopping of the investigational protocol, and reappearance of the reaction on repeated exposure.

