3 STUDY DESIGN

3.1 Overall Study Design and Plan

This single-site, open-label trial will investigate the effects of BCG vaccination on IIR and AD biofluid biomarkers, magnetic resonance imaging (MRI) biomarkers, and neurocognitive/behavioral functioning over a one-year period in older adults with mild cognitive impairment (MCI) to mild-to-moderate dementia due to AD. This study will also gather data on tolerability and safety. Safety will continue to be followed in the second year by phone.

Up to twenty five participants meeting eligibility criteria will be enrolled. Each participant will receive two intradermal BCG vaccinations spaced 4-6 weeks apart and will be evaluated 12, 26, and 52 weeks after the initial immunization. Cerebrospinal fluid (CSF), blood, MRI (in a subset of patients), and neurocognitive/behavioral assessments will be collected at Screening (CSF, blood, and cognitive/behavioral), Week 1 (MRI and cognitive/behavioral), Week 4 (blood), Week 12 (CSF, blood, and cognitive/behavioral), Week 26 (Blood and cognitive/behavioral) and Week 52 (all) to assess biomarkers and safety. Safety measures, including updated medical history and adverse events, will be collected at Week 78 and Week 104.

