7.7.2 Warnings

BCG contains live, attenuated mycobacteria, and carries risk for adverse consequences particularly in immunocompromised individuals for whom the attenuated strain could become pathogenic as described below (section 9.1, BCG vaccine risks).

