11.3.6 Adverse Events and Serious Adverse Events - Reportable Events

All events that meet the above criteria for Serious Adverse Events must be reported to the IRB within 24 hours of a study investigator being notified of the event.

Any adverse reaction that is serious, unexpected, and associated with the use of the product will be reported to the FDA in an IND safety report no more than 15 calendar days after the PI determines that the suspected adverse reaction qualifies for reporting, or 7 days for unexpected fatal or life-threatening adverse reaction reports.

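### For BCG reactions first arising after dose 2, the causality definitions in section 11.3.4 cap the rating at Possibly Related and leave a well-timed reaction with no known pattern without any category

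*Combined protocol and SAP*

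**What the plan says.** Section 11.3.4 of the combined protocol and SAP gives a five-step scale. Not Related applies when nothing reasonably links the event to the protocol. Unlikely applies when the timing is poor, when another cause is more probable, or both. Possibly Related asks for reasonable timing "and follows a known response pattern to the suspected investigational protocol". Probably Related asks for a well-timed reaction that the subject's clinical state cannot reasonably explain and that "is confirmed by discontinuation of the investigational protocol or by re-challenge". Definitely Related asks for timing, a known or expected pattern, and a reaction "that is confirmed by improvement on stopping of the investigational protocol, and reappearance of the reaction on repeated exposure".

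The product and schedule are fixed elsewhere. Section 7.7.2: "BCG contains live, attenuated mycobacteria". Section 3.1: "Each participant will receive two intradermal BCG vaccinations spaced 4-6 weeks apart".

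Causality also appears in other places. Section 8.2 plans adverse event tables by relationship to study treatment, but does not say which of the five steps make an event related. Section 11.3.1.1 makes the principal investigator responsible for "determining if there is reasonable possibility that the drug was the cause". Section 11.3.1 defines the unexpected: "An unexpected adverse event is any adverse event, the specificity or severity of which is not consistent with the current product insert". Section 11.3.6 then says: "Any adverse reaction that is serious, unexpected, and associated with the use of the product will be reported to the FDA". Section 11.3.4 rates relation to the investigational protocol, whereas 11.3.5 records relation to the investigational product.

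**The concern.** The scale is written for a treatment that can be stopped and restarted. An injected live vaccine cannot be withdrawn, and after dose 2 no further exposure is planned. Taken literally, the definitions then make a strong attribution impossible however clear the case, and they offer nothing for a new kind of reaction that has no better explanation.

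This matters because safety and tolerability is the first primary objective (section 3.2), and every participant receives BCG. With no concurrent control arm, the investigator's attribution is the main means of separating vaccine effects from background illness. If the related-event tables in 8.2 look sparse because of how the categories are defined, a reader could take that as reassurance the data do not give.

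**Working it through.** The plan states no figure on this point. The check sets the five definitions against what can be observed after each dose.

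*Inputs*
- Doses: two (section 3.1). Section 6.1.1 also gives roll-over participants two BCG doses in total.
- Dose 2: 28 (+14) days after dose 1, so 28 to 42 days (section 6.2.3).
- Last scheduled safety contact: nominal Day 728 (section 6.2.8).
- Dose 2 is withheld after the events listed in section 5.3.2.
- Disseminated BCG infection usually presents 4 months to 2 years after vaccination (section 5.3.2).

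*Step 1: which categories can be met.* Take a BCG reaction with plausible timing, and read plausible timing with no better cause as enough to rule out Not Related.

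| Situation | Known pattern? | More likely cause? | Categories met |
|---|---|---|---|
| First arises after dose 2 | Yes | No | Possibly |
| First arises after dose 2 | No | No | None |
| First arises after dose 2 | No | Yes | Unlikely |
| After dose 1, dose 2 withheld, event improves | No | No, and clinical state does not explain it | Probably, if withholding counts as discontinuation |
| After dose 1, dose 2 given, event recurs | No | No, and clinical state does not explain it | Probably |
| After dose 1, dose 2 given, improvement and recurrence both seen | Yes | No, and clinical state does not explain it | Possibly, Probably and Definitely |

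No combination after dose 2 reaches Probably or Definitely for BCG. The row with no category arises because Possibly fails on pattern, Probably and Definitely fail on confirmation, and Unlikely fails because the timing is good and no other cause is more likely.

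*Step 2: how much of follow-up lies after dose 2.*
- Dose 2 at 28 days: 728 − 28 = 700; 700/728 = 96.2%.
- Dose 2 at 42 days: 728 − 42 = 686; 686/728 = 94.2%.

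This is a share of calendar time only.

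*Step 3: a late known reaction.* Four months is about 4 × 30.44 = 122 days, later than the latest dose 2 at 42 days. Disseminated infection in its usual window therefore first arises after dose 2. As a risk listed in section 9.1 it has a known pattern, so it reaches Possibly and goes no higher.

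*Step 4: what one participant is worth in the related tables.* Section 8.1 gives about 15 subjects: 1/15 = 6.7 percentage points. With the 12 expected completers (section 4.2) it is 1/12 = 8.3, and with the maximum of 25 (section 3.1) it is 1/25 = 4.0. These show the weight of a single reclassification; they do not estimate how many would occur.

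**The case against.** The strongest reply is that little of the safety system rests on this scale, and much of that reply stands. The primary safety endpoint in 8.2, the incidence of Grade II-IV events, has no causality filter. Section 11.3.6 sends all serious events to the IRB within 24 hours whatever their cause. The pause and stopping rules in 5.5 do not refer to the scale.

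Several stronger readings are tempting, and the documents do not support them.

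- *A new serious reaction would be kept from the FDA.* Nothing makes 11.3.4 the gate for 11.3.6. The trigger there is the principal investigator's determination, and 11.3.1.1 supplies a reasonable-possibility test that could still lead to an IND report. Also, *unexpected* covers severity as well as kind, so some unexpected events will have a known pattern and reach Possibly.
- *The rule for withholding dose 2 is undermined.* Section 5.3.2 acts before dose 2. Only its first criterion speaks of attribution to BCG, and no text ties that to the scale.
- *No event after dose 2 can be rated above Possibly.* The scale covers the whole investigational protocol. Lumbar punctures at Weeks 12 and 52 and research blood draws at Weeks 12, 26 and 52 can be stopped or repeated. The limit concerns BCG reactions.
- *Any new kind of reaction is unclassifiable.* After dose 1 it can reach Probably, as the table shows.
- *About 95% of reactions are affected.* The 94% to 96% is days. Section 9.1 puts initial skin lesions at 10 to 14 days and systemic effects at 1 to 2 days' duration, so many dose 1 reactions will appear before dose 2.
- *A near-empty Probably or Definitely column is planned output.* Section 8.2 plans tables of related events and does not promise a column for each step.

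What the reply does not remove is the wording. Correct attribution after dose 2 would depend on the investigator setting aside the protocol's own definitions.

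**Conclusion.** The concern holds for BCG reactions that first arise after dose 2. Probably and Definitely Related cannot be reached. Known-pattern reactions are capped at Possibly, and a well-timed reaction with no more likely cause and no known pattern meets none of the five definitions.

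The consequence falls on the related-event tables in 8.2. Known-pattern reactions drop out only if Possibly is not counted as related, which 8.2 leaves open. Reactions that fit no category have no defined place in those tables under any cut-off. The direction is towards understating BCG-related events. The amount cannot be estimated from the documents.

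This rests on reading the definitions literally and on there being no BCG dose after the second. The point deserves correction, but it does not put the primary safety endpoint or the serious-event reporting to the IRB at risk, so it ranks below the changes the trial could not proceed without.

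**What to change.** In section 11.3.4, for relation to BCG:

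1. Remove improvement on stopping and recurrence on re-exposure as required conditions. Keep them as supporting evidence where they happen to be available.
2. Remove the known response pattern as a requirement for Possibly Related.
3. Base the categories on the reasonable-possibility test already in 11.3.1.1, graded by timing, alternative causes and supporting findings (for example, location at the injection site or regional nodes, or identification of BCG).
4. Rate relation to BCG separately from relation to study procedures, and reconcile the term used in 11.3.4 (protocol) with the one in 11.3.5 (product).

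In section 8.2, state that Possibly, Probably and Definitely Related together count as related.

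Reconcile the causality wording across 5.3.2, 11.3.1.1, 11.3.4 and 11.3.6, so that a reader knows which judgement serves which purpose. When dose 2 is withheld is a clinical matter for the sponsor and investigator, and nothing here proposes a rule for it.

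The cost is protocol wording and adverse event log instructions, plus re-rating of any events already classified under the present text. Doses, visits and sample size are untouched. The small downside is that more events will be classed as related.
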